11.1.1 Definitions

Evaluable for Target Disease response. Only those participants who have leptomeningeal disease present at baseline (as defined by positive cytology), have received at least one cycle of therapy, and have had their disease re-evaluated with restaging scans and cytology will be considered evaluable for target disease response. These participants will have their response classified according to the definitions stated below.

Evaluable Non-Target Disease Response. Participants who have lesions present at baseline that are evaluable but do not meet the definitions of measurable disease, have received at least one cycle of therapy, and have had their disease re-evaluated will be considered evaluable for non-target disease. The response assessment is based on the presence, absence, or unequivocal progression of the lesions.

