- 3.1.7. Women of childbearing potential must have a negative serum or urine pregnancy test (minimum sensitivity 25 IU/L or equivalent units of HCG) within 72 hours prior to the start of nivolumab.
- 3.1.8. Women must not be breastfeeding.
- 3.1.9. Men who are sexually active with WOCBP must use any contraceptive method with a failure rate of less than 1% per year. Men receiving nivolumab and who are sexually active with WOCBP will be instructed to adhere to contraception for a period of 31 weeks after the last dose of investigational product. Women who are not of childbearing

potential, ie, who are postmenopausal or surgically sterile as well as azoospermic men do not require contraception

- 3.1.7 Ability to understand and the willingness to sign a written informed consent document.
- 3.1.8 Stable dose of dexamethasone 2 mg or less for 7 days prior to initiation of treatment
- 3.1.9 Carcinomatous meningitis, as defined by positive cytology or biopsy. If CSF cytology is negative, but imaging is consistent with carcinomatous meningitis, patient is eligible.

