5. TREATMENT PLAN

5.1 Treatment Regimen by histology:

For melanoma: patients will be treated with the combination regimen of nivolumab 1 mg/kg combined with ipilimumab 3mg/kg Q3W (4 doses), followed by nivolumab monotherapy (480 mg Q4W) until progression or unacceptable toxicity.

For nonsmall cell lung cancer and head and neck cancer: patients will be treated with nivolumab 3mg/kg Q2W + ipilimumab 1mg/kg Q6W

For small cell lung cancer, breast cancer, and bladder cancer: patients will be treated with nivolumab 1mg/kg + ipilimumab 3mg/kg Q3W x 4 doses, followed by nivolumab 240 mg Q2W

For renal cell carcinoma and other solid tumors (not listed above): patients will be treated with nivolumab 3mg/kg + ipilimumab 1mg/kg Q3W x 4 doses, followed by nivolumab 480 mg Q4W

Each treatment cycle will be 6 weeks, with the exception of the nivolumab maintenance monotherapy phase in melanoma, renal cell carcinoma and other solid tumors, when each cycle will be 8 weeks. Treatment will be administered on an outpatient basis. Reported adverse events and potential risks are described in Section 7. Appropriate dose modifications are described in Section 6. No investigational or commercial agents or therapies other than those described below may be administered with the intent to treat the participant's malignancy.

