11.1.2 Disease Parameters

Measurable disease. Measurable lesions are defined as those that can be accurately measured in at least one dimension (longest diameter to be recorded) as ≥ 20 mm by chest x-ray or ≥ 10 mm with CT scan, MRI, or calipers by clinical exam. All tumor measurements must be recorded in millimeters (or decimal fractions of centimeters).

Note: Tumor lesions that are situated in a previously irradiated area might or might not be considered measurable.

Malignant lymph nodes. To be considered pathologically enlarged and measurable, a lymph node must be ≥ 15 mm in short axis when assessed by CT scan (CT scan slice thickness recommended to be no greater than 5 mm). At baseline and in follow-up, only the short axis will be measured and followed.

Non-measurable disease. All other lesions (or sites of disease), including small lesions (longest diameter <10 mm or pathological lymph nodes with ≥ 10 to <15 mm short axis), are considered non-measurable disease. Bone lesions, leptomeningeal disease, ascites, pleural/pericardial effusions, lymphangitis cutis/pulmonitis, inflammatory breast disease, abdominal masses (not followed by CT or MRI), and cystic lesions are all considered non-measurable.

Note: Cystic lesions that meet the criteria for radiographically defined simple cysts should not be considered as malignant lesions (neither measurable nor non-measurable) since they are, by definition, simple cysts.

‘Cystic lesions’ thought to represent cystic metastases can be considered as measurable lesions, if they meet the definition of measurability described above. However, if non-cystic lesions are present in the same participant, these are preferred for selection as target lesions.

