Target lesions. All measurable lesions up to a maximum of 2 lesions per organ and 5 lesions in total, representative of all involved organs, should be identified as **target lesions** and recorded and measured at baseline. Target lesions should be selected on the basis of their size (lesions with the longest diameter), be representative of all involved organs, but in addition should be those that lend themselves to reproducible repeated measurements. It may be the case that, on occasion, the largest lesion does not lend itself to reproducible measurement in which circumstance the next largest lesion which can be measured reproducibly should be selected. A sum of the diameters (longest for non-nodal lesions, short axis for nodal lesions) for all target lesions will be calculated and reported as the baseline sum diameters. If lymph nodes are to be included in the sum, then only the short axis is added into the sum. The baseline sum diameters will be used as reference to further characterize any objective tumor regression in the measurable dimension of the disease.

Non-target lesions. All other lesions (or sites of disease) including any measurable lesions over and above the 5 target lesions should be identified as **non-target lesions** and should also be recorded at baseline. Measurements of these lesions are not required, but the presence, absence, or in rare cases unequivocal progression of each should be noted throughout follow up.

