11.2.1 Definitions

Evaluable for objective response. Only those participants who have measurable CNS disease present at baseline, have received at least one cycle of therapy, and have had their disease re-evaluated will be considered evaluable for target disease response in the CNS. These participants will have their response classified according to the definitions stated below. (Note: Participants who exhibit objective disease progression prior to the end of cycle 1 will also be considered evaluable.)

Evaluable non-measurable evaluable disease. Participants who have lesions present at baseline that are evaluable but do not meet the definitions of measurable disease, have received at least one cycle of therapy, and have had their disease re-evaluated will be considered evaluable for non-target disease. The response assessment is based on the presence, absence, or unequivocal progression of the lesions.

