11.4 Other Response Parameters

Cerebrospinal Fluid: Cerebrospinal fluid will collected as part of clinical care.

Leptomeningeal response will be defined as below:

Response	Cytologic	Neurologic	Radiographic
Complete Response	Reversion to (-) CSF cytology (or NA)	Disappearance of all disease related symptoms present prior to therapy (or NA)	Complete disappearance of all detectable radiographic EOD (or NA)
Partial Response	> 50% decrease in malignant CSF cytology	Improvement in neurologic symptoms or no worsening of symptoms	Improvement in radiographic evidence of disease. No new sites of measurable or assessable CNS disease
Stable Disease	Not fulfilling the criteria for CR or PR, but not progressive disease	Not fulfilling the criteria for CR or PR, but not progressive disease	Not fulfilling the criteria for CR, or PR but is not progressive disease
Progressive Disease	> 50% increase in malignant CSF cytology	Development of new neurologic symptoms related to neoplastic meningitis	Increase in radiographic evidence of disease. Appearance of new sites of disease.

Leptomeningeal response will be a secondary outcome.

The immune related Response Criteria (irRC) will also be used in this study to support secondary efficacy endpoints for extracranial lesions. Definitions of the immune-related Response Criteria (irRC) are below and are presented in Appendix B:

- Complete Response (CR): Disappearance of all lesions in two consecutive observations not less than 4 wk apart
- Partial Response (PR): $\geq 50\%$ decrease in tumor burden compared with baseline in two observations at least 4 wk apart
- Stable Disease (SD): 50% decrease in tumor burden compared with baseline cannot be established nor 25% increase compared with nadir
- Progressive Disease (PD): At least 25% increase in tumor burden compared with nadir (at any single time point) in two consecutive observations at least 4 wk apart

Index Lesion	Non-Index Lesion	New Measurable Lesions	New unmeasurable lesions	% change in tumor burden	Overall IR Response
CR	CR	No	No	-100%	irCR
PR	Any	Any	Any	$\geq -50\%$	irPR
PR	Any	Any	Any	$< -50\% \text{ to } < 25\%$	irSD
PR	Any	Any	Any	$\geq +25\%$	irPD
SD	Any	Any	Any	$< -50\% \text{ to } < +25\%$	irSD
SD	Any	Any	Any	$\geq +25\%$	irPD
PD	Any	Any	Any	$\geq +25\%$	irPD

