13.1 Study Design/Endpoints

Primary endpoint: Rate of overall survival at 3 months

Secondary Endpoints:

1. Toxicity by CTCAE criteria (grade 3 or higher hematologic toxicity; grade 3 or higher neurologic toxicity)
2. Intracranial response in patients with leptomeningeal metastases
3. Extracranial response as determined by RECIST and irRC
4. Leptomeningeal disease response as defined in section 11.4
5. Time to the first occurrence of extracranial disease progression, or death from any cause
6. Time to the first occurrence of intracranial disease progression, or death from any cause

Exploratory Endpoints: Genetic alterations

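### Section 11.1.1 decides who is evaluable for extracranial target response by positive CSF cytology instead of measurable extracranial lesions, and Section 13.6 gives that rate no denominator of its own

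*Combined protocol and SAP*

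**What the plan says.** Section 11.1 covers extracranial lesions under RECIST 1.1. For target disease response, 11.1.1 admits "Only those participants who have leptomeningeal disease present at baseline (as defined by positive cytology), have received at least one cycle of therapy", and requires that disease was then reassessed with both scans and cytology. No extracranial lesion is required.

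Section 11.1.2 lists as non-measurable "Bone lesions, leptomeningeal disease, ascites, pleural/pericardial effusions" and other sites. Target lesions are "All measurable lesions up to a maximum of 2 lesions per organ and 5 lesions in total, representative of all involved organs".

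Section 3.1 does not insist on positive cytology: "If CSF cytology is negative, but imaging is consistent with carcinomatous meningitis, patient is eligible". Biopsy is also accepted.

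The intracranial counterpart, 11.2.1, requires measurable CNS disease and adds: "Participants who exhibit objective disease progression prior to the end of cycle 1 will also be considered evaluable". Section 11.1.1 has no such note. On timing, Section 5.1 says "Each treatment cycle will be 6 weeks" (8 weeks in some maintenance phases), and 11.1 sets restaging every 6 weeks.

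Section 13.6 says that extracranial response by RECIST and by irRC will be summarised with 90% exact intervals. It gives no n and no analysis set for these rates. Its precision statement for 18 patients is attached to intracranial and leptomeningeal response only. Section 13.8 defines sets for toxicity and the primary endpoint only.

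**The concern.** The evaluability rule tests for a disease that cannot supply a RECIST target lesion and does not test for one that can. An analyst who needs a denominator for the extracranial rate finds no other rule for target disease. Two analysts, one following 11.1.1 literally and one using measurable extracranial disease, would report different rates from the same data.

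The conditions of one cycle and completed restaging, with no exception for early progression, add a second problem. Survival in this population is short, so patients who die or progress before the first restaging would leave the denominator, although none of them is a recorded responder. A single-arm trial has no control group to expose the resulting distortion.

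**Working it through.** **1. The plan's own precision figure.** Clopper-Pearson 90% limits are the 0.05 quantile of Beta(x, n−x+1) and the 0.95 quantile of Beta(x+1, n−x). At n = 18 the widest interval is at x = 9: 0.291 to 0.709, width 0.418. The stated 0.42 reproduces. It is not stated for the extracranial rate. For smaller sets (assumed sizes), the maximum width is 0.51 at n = 12 and 0.61 at n = 8.

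**2. Who the rule selects.** Cross baseline cytology with measurable extracranial disease, for patients who complete a cycle and are restaged by scans and cytology:

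| Baseline cytology | Measurable extracranial lesion | RECIST target response possible (11.1.2) | Evaluable under 11.1.1 |
|---|---|---|---|
| Positive | Yes | Yes | Yes |
| Positive | No | No | Yes |
| Negative (eligible by imaging or biopsy) | Yes | Yes | No |
| Negative (eligible by imaging or biopsy) | No | No | No |

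The second and third rows are wrong, in opposite directions.

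**3. Early loss (illustration).** Inputs from Section 13.2: 3-month survival of 18% (null) or 43% (alternative), and median survival of 2 to 4 months. Assumption: exponential survival, with 3 months = 13 weeks, 2 months = 8.67 weeks and 4 months = 17.33 weeks. The proportion dead before 6 weeks is 1 − S(6):

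- 18% at 3 months: 1 − 0.18^(6/13) = 1 − 0.453 = 55%
- Median 2 months: 1 − 0.5^(6/8.67) = 1 − 0.619 = 38%
- 43% at 3 months: 1 − 0.43^(6/13) = 1 − 0.677 = 32%
- Median 4 months: 1 − 0.5^(6/17.33) = 1 − 0.787 = 21%

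Section 3.1 requires a life expectancy above 3 weeks. If nobody died before week 3 and the hazard were constant afterwards, the losses would be smaller: 1 − 0.18^(3/10) = 40% at the high end and 1 − 0.5^(3/14.33) = 14% at the low end.

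**4. Direction.** Let n be the treated patients with measurable extracranial lesions, r the responders, and d those who die or progress before restaging. The rate moves from r/n to r/(n − d), which is larger whenever r and d are both above zero. The documents do not give n, and r and d are unknown at the planning stage, so the size of the shift cannot be stated. The misplaced cytology condition has no fixed direction: admitting patients without a target lesion lowers the rate, while excluding cytology-negative patients could move it either way.

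**The case against.** The strongest reply is that 13.6 never refers to 11.1.1, so nothing says the defective rule will be used, and a sensible analyst would take patients with measurable extracranial disease. That stands as far as it goes: the bias is conditional on the rule being applied. But 13.6 offers nothing in its place, and the definition as written is wrong whether or not it is used.

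A reader might also infer more than the documents support:

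- *That leptomeningeal response is limited to cytology-positive patients, contradicting eligibility.* Section 13.1 lists "Leptomeningeal disease response as defined in section 11.4", not 11.1.1, and the cytologic entry for complete response there begins "Reversion to (-) CSF cytology (or NA", which leaves room for patients without a cytology result to revert. The remaining gap is that 13.6 does not name the analysis set.
- *That intracranial response has the same fault.* Section 11.2.1 requires measurable CNS disease and keeps early progressors, and 11.2.4.1 counts failure to return because of death or deterioration as progression.
- *That non-sustained intracranial responses might be counted as partial responses because 11.2.4.2 still records them.* Section 11.2.4.1 already treats a partial response without a confirming scan as stable disease.
- *That the inflation can be sized from the planned 18 or 20 patients.* Those numbers are not the extracranial denominator. Nor does the plan say that receiving one cycle means being alive at week 6.

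**Conclusion.** The point holds for extracranial response. As written, 11.1.1 applies a cytology test that does not fit RECIST target disease, omits the early-progression exception found in 11.2.1, and is the only rule available for a rate to which 13.6 gives no n or analysis set. If it is applied, early loss biases the rate upward by an amount that the documents do not allow to be computed. The 21% to 55% figure for deaths before 6 weeks illustrates how common early loss could be. It rests on exponential survival and on patients with extracranial disease surviving like the whole cohort; it is not an estimate of the bias.

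The affected endpoints are secondary and descriptive. The 3-month survival decision rule does not use 11.1.1 and is unaffected. The correction should be made before the response analysis.

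**What to change.** Rewrite the whole target-disease sentence in 11.1.1. Remove the baseline cytology condition, the repeat cytology and the one-cycle requirement, together with the condition that restaging was completed. Patients evaluable for extracranial target response are then all treated patients with measurable extracranial lesions at baseline. Changing the cytology condition alone would leave the other clauses in conflict with an all-treated denominator.

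In 13.6:

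- Name this set as the denominator of the extracranial rate, using the measurability rule of 11.1.2 for the RECIST rate and that of Appendix B for the irRC rate, since one is unidimensional and the other bidimensional.
- Report separately any complete response in patients with only non-measurable extracranial disease, which 11.1.4.4 allows.
- Count death, progression or no post-baseline assessment as non-response.
- For leptomeningeal response, keep the criteria of 11.4 and state the denominator as all treated patients with leptomeningeal disease by cytology, biopsy or imaging, with the same non-response rule.

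The 0.42 width is correct for 18 patients and can stay where it is. The cost is wording in two sections, with no new data or visits. Reported response rates may be lower.

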11.1.2 Disease Parameters

Measurable disease. Measurable lesions are defined as those that can be accurately measured in at least one dimension (longest diameter to be recorded) as ≥ 20 mm by chest x-ray or ≥ 10 mm with CT scan, MRI, or calipers by clinical exam. All tumor measurements must be recorded in millimeters (or decimal fractions of centimeters).

Note: Tumor lesions that are situated in a previously irradiated area might or might not be considered measurable.

Malignant lymph nodes. To be considered pathologically enlarged and measurable, a lymph node must be ≥ 15 mm in short axis when assessed by CT scan (CT scan slice thickness recommended to be no greater than 5 mm). At baseline and in follow-up, only the short axis will be measured and followed.

Non-measurable disease. All other lesions (or sites of disease), including small lesions (longest diameter <10 mm or pathological lymph nodes with ≥ 10 to <15 mm short axis), are considered non-measurable disease. Bone lesions, leptomeningeal disease, ascites, pleural/pericardial effusions, lymphangitis cutis/pulmonitis, inflammatory breast disease, abdominal masses (not followed by CT or MRI), and cystic lesions are all considered non-measurable.

Note: Cystic lesions that meet the criteria for radiographically defined simple cysts should not be considered as malignant lesions (neither measurable nor non-measurable) since they are, by definition, simple cysts.

‘Cystic lesions’ thought to represent cystic metastases can be considered as measurable lesions, if they meet the definition of measurability described above. However, if non-cystic lesions are present in the same participant, these are preferred for selection as target lesions.

Target lesions. All measurable lesions up to a maximum of 2 lesions per organ and 5 lesions in total, representative of all involved organs, should be identified as **target lesions** and recorded and measured at baseline. Target lesions should be selected on the basis of their size (lesions with the longest diameter), be representative of all involved organs, but in addition should be those that lend themselves to reproducible repeated measurements. It may be the case that, on occasion, the largest lesion does not lend itself to reproducible measurement in which circumstance the next largest lesion which can be measured reproducibly should be selected. A sum of the diameters (longest for non-nodal lesions, short axis for nodal lesions) for all target lesions will be calculated and reported as the baseline sum diameters. If lymph nodes are to be included in the sum, then only the short axis is added into the sum. The baseline sum diameters will be used as reference to further characterize any objective tumor regression in the measurable dimension of the disease.

Non-target lesions. All other lesions (or sites of disease) including any measurable lesions over and above the 5 target lesions should be identified as **non-target lesions** and should also be recorded at baseline. Measurements of these lesions are not required, but the presence, absence, or in rare cases unequivocal progression of each should be noted throughout follow up.

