11. MEASUREMENT OF EFFECT

Response in the CNS and response in non-CNS sites will be evaluated and recorded separately in this trial.

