11.1.4.2 Evaluation of Non-Target Lesions

Complete Response (CR): Disappearance of all non-target lesions and normalization of tumor marker level. All lymph nodes must be non-pathological in size (<10 mm short axis).

Note: If tumor markers are initially above the upper normal limit, they must normalize for a patient to be considered in complete clinical response.

Non-CR/Non-PD: Persistence of one or more non-target lesion(s) and/or maintenance of tumor marker level above the normal limits.

Progressive Disease (PD): Appearance of one or more new lesions and/or *unequivocal progression* of existing non-target lesions. *Unequivocal progression* should not normally trump target lesion status. It must be representative of overall disease status change, not a single lesion increase.

Although a clear progression of “non-target” lesions only is exceptional, the opinion of the treating physician should prevail in such circumstances, and the progression status should be confirmed at a later time by the review panel (or Principal Investigator).

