APPENDIX B

TUMOR ASSESSMENT PER IMMUNE-RELATED RESPONSE CRITERIA

Immune-related Response Criteria (irRC) are derived from modified World Health Organization (mWHO) conventions. Assessments of lymph nodes are derived from current RECIST guidelines.

Definitions of Measurable/non-Measurable Lesions

All measurable and non-measurable lesions should be assessed at Screening and at the defined tumor assessment time points. Additional assessments may be performed, as clinically indicated for suspicion of progression.

Measurable Lesions

Measurable lesions are lesions that can be accurately measured in 2 perpendicular diameters, with at least 1 diameter ≥ 20 mm and the other dimension ≥ 10 mm (10 mm x 10 mm for spiral CT with cuts of 5 mm). The area will be defined as the product of the largest diameter with its perpendicular.

Lymph nodes may also be considered measurable. To be considered pathologically enlarged and measurable, a lymph node must be at least 15 mm in short axis when assessed by CT scan (CT scan slice thickness recommended to be no greater than 5 mm).

Non-Measurable Lesions

Non-measurable (evaluable) lesions are all other lesions, including unidimensional measurable disease and small lesions (lesions without at least 1 diameter ≥ 20 mm, or pathological lymph nodes with short axis $\square 15$ mm), and any of the following: lesions occurring in a previously irradiated area (unless they are documented as new lesions since the completion of radiation therapy), bone lesions, leptomeningeal disease, ascites, pleural or pericardial effusion, lymphangitis cutis/pulmonis, abdominal masses that are not pathologically/cytologically confirmed and followed by imaging techniques and cystic lesions. Lymph nodes that have a short axis < 10 mm are considered non-pathological and should not be recorded or followed.

Definitions of Index/non-Index Lesions

Index Lesions

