Measurable lesions, up to a maximum of 5 lesions per organ and ten lesions in total, must be identified as index lesions to be measured at Screening. The index lesions should be representative of all involved organs. In addition, index lesions must be selected based on their size (eg, lesions with the longest diameters), their suitability for accurate repeat assessment by imaging techniques, and how representative they are of the subject's tumor burden. At Screening, a Sum of the Product Diameters (SPD) for all index lesions will be calculated and considered the baseline SPD. The baseline sum will be used as the reference point to determine the objective tumor response of the index lesions at tumor assessment.

Non Index Lesions

Measurable lesions, other than index lesions, and all sites of non-measurable disease, will be identified as non-index lesions. Non-index lesions will be evaluated at the same assessment time

points as the index lesions. In subsequent assessments, changes in non-index lesions will contribute only in the assessment of complete response.

Calculation of Sum of Product of Diameters (SPD)

Sum of Product of Diameters is an estimate of tumor burden. The 2 greatest perpendicular diameters are used to estimate the size of each tumor lesion. The SPD is calculated as the sum of the product of the diameters for index tumor lesions. Several variations of the SPD are identified for the purpose of classification of tumor responses.

SPD at Baseline: The sum of the product of the diameters for all index lesions identified at baseline prior to treatment on Day 1.

SPD at tumor assessment: For every on-study tumor assessment collected per protocol or as clinically indicated, the SPD at tumor assessment will be calculated using tumor imaging scans. All index lesions and all new measurable lesions that have emerged after baseline will contribute to the SPD at tumor assessment (irSPD).

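### The extracranial response rules (11.1 and Appendix B) do not exclude CNS sites and list leptomeningeal disease as a lesion, so on the RECIST text CNS progression can be scored as an extracranial PFS event

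*Combined protocol and SAP*

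**What the plan says.** **RECIST (Section 11.1, headed extracranial).** 11.1.2 names "Bone lesions, leptomeningeal disease, ascites, pleural/pericardial effusions, lymphangitis cutis/pulmonitis, inflammatory breast disease" among the non-measurable disease types. The same section continues: "All other lesions (or sites of disease) including any measurable lesions over and above the 5 target lesions should be identified as" non-target lesions, to be recorded at baseline. Under 11.1.4.2, non-target CR means "Disappearance of all non-target lesions and normalization of tumor marker level", and non-target PD means "Appearance of one or more new lesions and/or *unequivocal progression* of existing non-target lesions". 11.1.1 defines who is evaluable for target disease response by cytology-positive leptomeningeal disease at baseline and by restaging with scans and cytology.

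**irRC (Appendix B).** The non-measurable list includes "bone lesions, leptomeningeal disease, ascites, pleural or pericardial effusion", and "all sites of non-measurable disease, will be identified as non-index lesions". Non-index lesions count only towards complete response.

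**Separation of CNS and non-CNS.** Section 11 opens with "Response in the CNS and response in non-CNS sites will be evaluated and recorded separately". 11.3 sends brain MRI to RANO review and non-CNS scans to RECIST review. 11.4 gives leptomeningeal disease its own cytologic, neurologic and radiographic scale and applies irRC to extracranial lesions.

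**Endpoints.** 13.6 defines EPFS by extracranial progression under RECIST or irRC, or death. It summarizes extracranial response as CR or PR under each criterion.

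**The concern.** Eligibility item 3.1.9 requires carcinomatous meningitis, so every participant carries the lesion that the extracranial rules name. Secondary objectives 3 and 5 in Section 1.3 ask for systemic response and systemic PFS. They need body disease to be scored apart from CNS disease. If leptomeningeal or new brain lesions can enter the extracranial lesion set, an EPFS event may reflect CNS progression alone.

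The two criteria also treat leptomeningeal growth differently, and 13.6 joins them with 'or' without giving precedence. The same patient could have an EPFS event under one and not under the other.

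**Working it through.** The plan gives no figure to reproduce. The first check traces four hypothetical patients through the rules as written; the second gives a sense of scale under assumptions.

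**1. Rule tracing** (11.1.2, 11.1.4.2, the tables in 11.1.4.4, Appendix B)

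| Patient | RECIST on the text | irRC on the text |
|---|---|---|
| A. Liver targets stable, leptomeninges clearly worse | PD if the worsening is unequivocal and represents a change in overall disease status | Not irPD: non-index growth does not count unless measured burden rises 25% |
| B. Body disease stable, new brain metastasis | PD: any new lesion gives PD, and the overall-status limit is not attached to new lesions | Not irPD for being new; if measurable, it is added to the summed burden |
| C. Only bone disease outside the CNS, which disappears; leptomeningeal disease persists | Non-CR/non-PD, so not a responder (CR without the leptomeningeal lesion) | irCR blocked, and there is no measurable burden on which to reach irPR |
| D. Liver targets disappear, leptomeningeal disease persists | PR instead of CR, still a responder | irPR instead of irCR, still a responder |

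So the CR block holds under both criteria but by itself changes CR+PR status only for patients like C. The progression route is a RECIST matter: conditional for A, direct for B.

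**2. Scale of the EPFS effect**

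Inputs:
- Scans every 6 weeks (Section 10), taken as a 1.4-month grid, so the last scan before 3 months is at 2.8 months.
- Exponential times (assumed).
- Medians of 4 months for extracranial progression, 3 for leptomeningeal progression and 4 for death. The first two are assumptions. The third is the upper end of the 2 to 4 months in 13.2.
- Extracranial progression independent of the other two (assumed), and every leptomeningeal progression counted.

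A patient is event-free at 3 months if no progression has occurred by 2.8 months and no death by 3 months:

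- Extracranial: 0.5^(2.8/4) = 0.616
- Leptomeningeal: 0.5^(2.8/3) = 0.524
- Alive: 0.5^(3/4) = 0.595

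3-month EPFS:

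- Leptomeningeal progression excluded: 0.616 × 0.595 = 0.37
- Counted, all independent: 0.616 × 0.524 × 0.595 = 0.19
- Counted, leptomeningeal progression and death fully dependent: 0.616 × min(0.524, 0.595) = 0.32

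Other assumed medians, by the same formulas:

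| Medians (months) | Excluded | Counted, independent | Counted, fully dependent |
|---|---|---|---|
| 4/3/4 | 0.37 | 0.19 | 0.32 |
| 6/3/5 | 0.48 | 0.25 | 0.38 |
| 4/4/6 | 0.44 | 0.27 | 0.38 |

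Section 2.1 says that death usually follows rapid neurologic deterioration, so independence is unlikely to describe this disease. If few leptomeningeal events are actually scored as extracranial, the result moves back towards the first column.

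**The case against.** The strongest reply is that the scope is stated several times. Section 11.1 is headed extracranial, the opening of Section 11 separates CNS from non-CNS response, 11.3 gives only non-CNS scans to the RECIST reviewers, 11.4 supplies a leptomeningeal scale, and 13.6 defines intracranial PFS separately. On this view the list in 11.1.2 is generic measurability text, and a central reviewer of body scans has little reason to record a leptomeningeal or brain lesion.

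Much of this stands as evidence of intent, and it limits how often the problem would arise. It does not remove the conflict. The opening sentence speaks of response rather than progression and gives no lesion rule. 11.1.1 brings leptomeningeal disease and cytology into the extracranial section itself. 11.1.4.2 lets the treating physician's opinion prevail on non-target-only progression, subject to later confirmation. Appendix B bases key efficacy endpoints on investigator-defined irRC.

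A reader might also infer that leptomeningeal progression is automatically extracranial progression under both criteria, so that EPFS collapses into overall PFS. The documents do not support that. Appendix B says that non-index growth, and new lesions alone, are not irPD. 11.1.4.2 says non-target progression should not normally override target status and must represent overall disease status. Nor does a blocked CR generally lower the response rate: where targets have disappeared, the table in 11.1.4.4 gives PR.

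**Conclusion.** The point holds as a conflict between sections. The extracranial lesion rules name leptomeningeal disease and exclude no CNS site, while the opening of Section 11, 11.3 and 11.4 call for separate assessment. The main exposure is EPFS under RECIST, together with the unstated precedence between RECIST and irRC. The CR block is real under both criteria but minor for the CR+PR rate.

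Only secondary endpoints, planned for about 18 patients, are touched; 3-month overall survival is not. The fall from 0.37 to between 0.19 and 0.32 illustrates possible scale and does not estimate this trial's effect. It rests on assumed medians, exponential times and every leptomeningeal progression being counted.

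**What to change.** 1. Add to 11.1.2 and Appendix B: *Brain parenchymal, leptomeningeal and spinal CNS lesions are not target, non-target, index, non-index or new lesions for extracranial RECIST/irRC; parenchymal brain lesions are scored under 11.2, and leptomeningeal disease (including spinal) under 11.4.*
2. Remove leptomeningeal disease from both non-measurable lists. This is not enough alone, because the catch-all for other lesions and disease sites would still capture it; item 1 does the work.
3. In 11.1.1, define evaluability by extracranial disease at baseline, and move the leptomeningeal and cytology definition to 11.4.
4. In 13.6, state whether RECIST or irRC governs EPFS.

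These are wording changes and need no new data. One consequence should be accepted knowingly: intracranial PFS uses RANO, and 11.2.4 has no cytologic progression criterion. Leptomeningeal progression seen only on cytology would therefore be recorded under 11.4 but enter neither PFS endpoint.
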